3.2.2 Main analytical approach

The individual statistical hypothesis for comparing each dose of SAR441566 vs. placebo on the primary endpoint at the two-sided significance level of 0.05 is as follows:

- Null hypothesis H0: The odds ratio between SAR441566 and placebo is equal to 1 when evaluating the primary endpoint,
- Alternative hypothesis H1: The odds ratio between SAR441566 and placebo is NOT equal to 1 when evaluating the primary endpoint.

The primary endpoint will be analyzed with the primary estimand defined according to the following attributes:

- Endpoint: Proportion of participants with a 75% or greater PASI score improvement from baseline at Week 12.
- Intervention condition: SAR441566 200 mg BID, 100 mg BID, 200 mg QD, 100 mg QD and 50 mg QD will be compared to placebo
- Analysis population: NTIP population
- Intercurrent events:
 - IMP discontinuation: it will be handled with the treatment policy strategy. The primary endpoint will be assessed based on all assessments irrespective of the IMP discontinuation.
 - Starting the selected concomitant medication (ie, prohibited/permited/rescue) (see [Table 4](#)): It will be handled with the composite variable strategy. For primary endpoint, participants who receive selected concomitant medications will be considered as non-responders for time points after the medication usage. For other participants, all available data including those collected during the off-treatment period will be used to determine the responder/non-responder status. Imputation rules of partial start dates of medication are detailed in [Section 5.6](#).

Blinded medical review of participants that receive the selected concomitant medication listed in [Table 4](#) will be performed before database lock by considering the type of medication, indication, timing, frequency, and the potential impact on efficacy to make the final decision about the list.

Table 4 - Selected prohibited/permited/rescue concomitant medications

Class of Medications	Selection Criteria	Composite variable strategy ¹
[REDACTED]		

Class of Medications	Selection Criteria	Composite variable strategy ¹

strategy. When no, a treatment policy strategy will be applied.

- Population-level summary: Difference in the percentage of participants achieving PASI75 response at Week 12 between each active arm and placebo. The Cochran-Mantel-Haenszel (CMH) test for odds ratio will be used for the primary endpoint analysis, adjusting for baseline disease severity defined by baseline PASI (≤ 20 , >20). The two-sided p-value based on CMH test for odds ratio and 95% confidence intervals (CI) based on Newcombe method (1) for Mantel-Haenszel treatment difference will be presented (SAS code example in [Section 5.4](#)) . Multiplicity adjustment will be provided (See [Section 3.5](#)).
- After applying the rules for the ICEs, the remaining missing data will be handled as follows:
 - Participants will be considered as non-responders.

3.2.3 Sensitivity analyses

Not applicable.

3.2.4 Supplementary analyses

The following supplementary analysis will be conducted to assess the robustness of the primary estimand.

- As observed analysis (including all data after taking selected concomitant medications)

The Cochran-Mantel-Haenszel analysis will be performed, but the data after taking the selected prohibited/permitted/rescue concomitant medications will be used in this supplementary analysis to evaluate the robustness of the primary analysis results with respect to the intercurrent event handling strategy. It implies that, in as observed analysis, treatment policy strategy will be used for all intercurrent events. Missing data will be imputed to non-responders when the response to PASI75 is missing.

3.2.5 Exploratory analyses

[figure not shown]
Dose-response relationship

For NTIP population, the dose-response relationship of QD doses will be evaluated by a 2-step MCP-Mod procedure (2, 3) on the primary endpoint among three QD doses (200 mg QD, 100 mg QD and 50 mg QD) vs. placebo. The first step of this procedure tests for an efficacy signal (compared to the null hypothesis of a flat, no dose-response curve) in a procedure. To account for the uncertainty of the dose-response shape, [REDACTED]

[REDACTED] (see Figure 2 on logit scale and Figure 3 on original scale). The second step is the estimation of the dose-response curve, provided that an efficacy signal is established in the first step.

A logistic regression model with covariates for PASI75 response rate, treatment and baseline severity will be used to assess the response rate of PASI75 in each of 3 QD dose groups and placebo group at the end of 12 weeks treatment. A logit transformation of the PASI75 response rate will be entered into the MCP-Mod procedure (see R code in Appendix 5.5). The null hypothesis of a flat dose-response curve (ie, no dose-response relationship) at the end of 12 weeks treatment for the primary endpoint will be jointly evaluated for each of the 6 candidate dose response models with a contrast test at 2-sided alpha = 0.05. If step 1 yields significant results, the best fitting model (smallest AIC) from the 6 predefined candidate models will be chosen using the generalized AIC. The suggested optimal dose will then be estimated from the final selected model.

3.3 SECONDARY ENDPOINT(S) ANALYSIS

The secondary endpoints detailed in this section are:

- PASI percent change from baseline to Week 12.
- Proportion of participants with sPGA score 0 (complete clearance) or 1 (minimal disease) at Week 12.

Other secondary endpoints analyses are defined in [Section 3.6.2](#) (AE, SAE), [Section 3.6.3.1](#) (laboratory abnormalities) and [Section 3.7.1.1](#) (PK).

3.3.1.1 Definition of endpoint(s)

➤ PASI percent change from baseline to Week 12

Please refer to [Section 3.2.1](#) for the definition of PASI. This secondary endpoint is the continuous endpoint to summarize the percent change of PASI at Week 12 comparing to the PASI at baseline.

➤ **Proportion of participants with sPGA score 0 (complete clearance) or 1 (minimal disease) at Week 12**

This secondary endpoint is the binary endpoint to summarize the proportion of participants with sPGA score 0 (complete clearance) or 1 (minimal disease) at Week 12, where sPGA score is defined as below.

static Psoriasis Global Assessment (sPGA)

The sPGA is a 5-point score ranging from 0 to 4, based on the physician's assessment of the average thickness, erythema, and scaling of all psoriatic lesions. The assessment is considered "static", which refers to the participant's disease state at the time of the assessments, without comparison to any of the participant's previous disease states, whether at Baseline or at a previous visit. A lower score indicates less body coverage, with 0 being clear and 1 being almost clear.

Erythema

- 0 Normal (post-inflammatory hyper/hypopigmentation may be present).
- 1 Faint, diffuse pink or slight red coloration.
- 2 Mild (light red coloration).
- 3 Definite red coloration (Dull to bright red).
- 4 Bright to Deep red coloration of lesions.

Induration (plaque elevation)

- 0 None.
- 1 Just detectable (slight elevation above normal skin).
- 2 Mild thickening (slight but definite elevation, typically edges are indistinct or sloped).
- 3 Clearly distinguishable to moderate thickening (marked definite elevation with rough or sloped edges).
- 4 Severe thickening with hard edges (marked elevation typically with hard or sharp edges).

Desquamation

- 0 No scaling.
- 1 Minimal focal scaling (surface dryness with some desquamation).
- 2 Predominately fine scaling (fine scale partially or mostly covering lesions).
- 3 Moderate scaling (coarser scale covering most or all of the lesions).

Overall Scoring resulting of the average of the Erythema, Induration and Desquamation score:

- Clear 0 = 0 for all three symptoms. Post-inflammatory hyper/hypopigmentation may be present.

- Almost clear 1 = mean $>0, <1.5$. Normal to pink coloration; just detectable (possible slight elevation above normal skin). No to minimal focal scaling.
- Mild 2 = mean $\geq 1.5, <2.5$. Pink to light red coloration; mild thickening (slight but definite elevation, typically edges are indistinct or sloped). Predominantly fine scaling.
- Moderate 3 = mean $\geq 2.5, <3.5$. Dull to bright red coloration; clearly distinguishable to moderate thickening; moderate scaling.
- Severe 4 = mean ≥ 3.5 . Bright to deep dark red coloration; severe thickening with hard edges; severe coarse scaling covering almost all or all lesions.

The sPGA overall score will be set to missing if any item is missing.

3.3.1.2 *Main analytical approach*

➤ PASI percent change from baseline to Week 12

This endpoint will be analyzed according to the following attributes:

- Endpoint: PASI percent change from baseline to Week 12
- Intervention condition: SAR441566 200 mg BID, 100 mg BID, 200 mg QD, 100 mg QD and 50 mg QD will be compared to placebo
- Analysis population: NTIP population
- Intercurrent events:
 - IMP discontinuation: it will be handled with the treatment policy strategy. This endpoint will be assessed based on all assessments irrespective of the IMP discontinuation.
 - Starting the selected concomitant medication (see [Table 4](#)): It will be handled with the composite variable strategy. For this endpoint, data after the selected concomitant medication use will be assigned using the worst post-baseline value on or before the time of the medication usage (ie, WOCF). For participants whose postbaseline values are all missing, the participant's baseline value will be used.
- Population-level summary: PASI score will be analyzed using an ANCOVA on the percent change from baseline in PASI at Week 12, including treatment as categorical effect and baseline value as continuous covariate. The least-squares means estimates of the percent changes from baseline at Week 12 in each treatment group and their corresponding two-sided 95% CI will be reported, as well as the differences between each SAR441566 groups and placebo in least square mean change from baseline (and 95% CIs) and p-values comparing the treatment groups. No multiplicity adjustment will be made.
- After applying the rules for the ICEs, the remaining missing data will be handled as follows:
 - “Worst observation carried forward” (WOCF) approach will be used to impute missing data

➤ **Proportion of participants with sPGA score 0 or 1 at Week 12**

This endpoint will be analyzed according to the following attributes:

- Endpoint: Proportion of participants with sPGA score 0 or 1 at Week 12.
- Intervention condition: SAR441566 200 mg BID, 100 mg BID, 200 mg QD, 100 mg QD and 50 mg QD will be compared to placebo
- Analysis population: NTIP population
- Intercurrent events:
 - IMP discontinuation: it will be handled with the treatment policy strategy. This endpoint will be assessed based on all assessments irrespective of the IMP discontinuation.
 - Starting the selected concomitant medication (see [Table 4](#)): It will be handled with the composite variable strategy. For this endpoint, participants who receive selected prohibited medications will be considered as non-responders for time points after the medication usage. For other participants, all available data including those collected during the off-treatment period will be used to determine the responder/non-responder status.
- Population-level summary: Difference in the percentage of participants with sPGA score 0 or 1 at Week 12 between each active arm and placebo. The CMH test will be used for this endpoint analysis, adjusting for baseline disease severity defined by baseline PASI (≤ 20 , > 20). The two-sided p-value based on CMH test for odds ratio and 95% confidence intervals (CI) based on Newcombe method ([1](#)) for Mantel-Haenszel treatment difference will be presented (SAS code example in [Section 5.4](#)). No multiplicity adjustment will be made.
- After applying the rules for the ICEs, the remaining missing data will be handled as follows:
 - Participants will be considered as non-responders

[figure not shown]

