- Proportion of participants with sPGA score of clear or almost clear (0 or 1) at Week 4 and 8

The following time to event endpoints will be estimated and presented using the Kaplan-Meier product-limit method:

- Time until the first achievement of PASI50, PASI75, PASI90, PASI100, sPGA of 0 or 1

Kaplan-Meier plots of time to event will also be presented. In these Kaplan-Meier plots, the line will start at 0 (since there are no event at Baseline) and will increase over time, representing time to event. The median time to event, including the two-sided 95% confidence interval, will be calculated. The estimates of the hazard ratio and 95% CI will be provided using a Cox Proportional Hazard Model stratified by the baseline PASI (≤ 20 , > 20). The censoring events include receiving selected concomitant medication or by the last assessment of targeted efficacy endpoint. The time at risk/time to event will be defined as follows:

1. If the subject has at least one event before receiving selected concomitant medication or by the last assessment of targeted efficacy endpoint, then time to event is defined as the first event date – the first dose date + 1.
2. If the subject does not have an event or receives selected concomitant medication before any event(s), the time at risk is defined as the minimum of (the last assessment date of targeted efficacy endpoint – the first dose date + 1, the date of receiving selected concomitant medication – the first dose date + 1).

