5.6 APPENDIX 6 IMPUTATION RULES FOR START DATES OF MEDICATION IN ICE

The date format is: YYYY-MM-DD

1. If the year is missing
 - No imputation can be done. Medication will be assumed to start prior to the randomization date. Set the date to one day before the randomization date.
2. If the month is missing and year is not missing
 - If year is equal to year of randomization date, then set the date of one day prior the randomization date
 - If year is not equal to year of randomization date, then Impute day and month with 01-January
3. If the day is missing and year and month are not missing:
 - Impute the day with 01
 - Exception: If the given year and month (YYYY-MM) correspond to the randomization date's year and month, impute one day before the randomization date.
 - Example:
 - If the IE start date is 2024-03, the imputed date is 2024-03-01.
 - However, if the randomization date is 2024-03-08, the imputed date will be 2024-03-07.

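### Do medication starts imputed to the day before randomization break the PASI percent-change and time-to-response rules?

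*SAP*

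**What the plan says.** SAP 5.6 sets a partial medication start to the day before randomization in three cases. With the year missing: "Set the date to one day before the randomization date". With the month missing: "If year is equal to year of randomization date, then set the date of one day prior the randomization date". With only the day missing, the same date applies if year and month match those of randomization; in the SAP's example, "However, if the randomization date is 2024-03-08, the imputed date will be 2024-03-07". A missing day in any other month becomes the first of that month.

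Two rules outside the binary endpoints use this date.

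- **PASI percent change, SAP 3.3.1.2.** Under the composite strategy, "data after the selected concomitant medication use will be assigned using the worst post-baseline value on or before the time of the medication usage". The next sentence of the same bullet is a fallback: "For participants whose postbaseline values are all missing", the baseline value is used. A separate closing item covers what is still missing once the intercurrent-event rules have been applied ("WOCF) approach will be used to impute missing data").
- **Time to first response, SAP 3.4.2.** The event is counted under the condition "If the subject has at least one event before receiving selected concomitant medication" or by the last assessment. For a participant who has no event, or who "receives selected concomitant medication before any event(s), the time at risk is defined as the minimum of" two intervals: first dose to last assessment, and first dose to medication, each plus 1 day.

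**The concern.** A date before randomization seems to leave both rules without a usable answer.

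For PASI percent change, no post-baseline value can be eligible. The fallback is worded for people with no post-baseline values at all, and someone measured at Weeks 4, 8 and 12 does not literally fit. Read mechanically, the text could pass to the general carry-forward item, which is not restricted to values before the medication. Two programmers might then report 0% or a value measured under another therapy.

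For time to response, the formula has no floor. A participant with 0 or negative days is in no risk set, and a response measured before the true start could be lost. The binary analyses keep the same participant in the denominator as a non-responder. At stake are one secondary endpoint and the exploratory curves and hazard ratios.

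**Working it through.** **Inputs.** Imputation rules and example: SAP 5.6. Baseline is the last value before first dose: SAP 3.1. Day 1 is both first intake and randomization: Protocol, list of abbreviations. PASI after baseline is planned on Days 29, 57 and 85 (±3): Protocol 1.3. Write R for randomization, F for first dose and M for the imputed medication date. Nominal visits are assumed, with no early end-of-treatment or unscheduled PASI.

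**1. The SAP's example.** R = 2024-03-08, start recorded as 2024-03: M = R − 1 = 2024-03-07, as the SAP states.

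**2. Eligible PASI values.** Post-baseline values lie at or after F, and F ≥ R > R − 1 = M. The eligible set is always empty.

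**3. The value that follows.** With M = R − 1, Weeks 4, 8 and 12 all fall after the medication, so the first sentence of the bullet replaces all of them. No post-baseline value is left, and the fallback in the next sentence gives baseline, that is 0% change. The rival reading has to blank Week 12 because it follows the medication, then carry forward another value that also follows it. If post-medication values are set aside, there is none to carry; if they are kept, a measured Week 12 is not missing. That reading contradicts the composite strategy stated in the bullet.

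**4. Who receives which date (R = 2024-03-08).** Day 24 is 2024-03-31, Day 25 is 2024-04-01 and Day 55 is 2024-05-01.

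| Missing part | True start | Imputed date | Effect on planned PASI before the true start |
|---|---|---|---|
| None | Days 1–28 | true date | none exists |
| Day | Days 1–24 | 2024-03-07 | none exists |
| Day | Days 25–54 | 2024-04-01 (Day 25) | Week 4 lost for Days 29–54: 54 − 29 + 1 = 26 start days |
| Day | Days 55–85 | 2024-05-01 (Day 55) | Week 4 still eligible |
| Month or year | Days 1–85 | 2024-03-07 | lost for Days 29–85: 85 − 29 + 1 = 57 start days |

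With the day missing, the pre-randomization date loses nothing here. The 26 start days come from the ordinary first-of-month convention. A complete date on Days 1–28 leaves the eligible set just as empty, so the gap in the fallback wording is not a product of SAP 5.6.

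The least favourable calendar is randomization on the first of a 31-day month, where the pre-randomization date covers Days 1–31. A Week 4 PASI on Day 29 could then precede true starts on Days 29–31 (3 start days), or 6 start days (26–31) if the visit took place on Day 26.

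**5. Time at risk.** M − F + 1 = (R − 1) − F + 1 = −(F − R). With F = R, min(85, 0) = 0. With F one, two or three days after R (assumed lags), the result is −1, −2 or −3.

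**6. Effect on the estimates.** The first possible event is at the first post-baseline PASI, nominally Day 29. A participant censored at 0, at 1, at the true day (24 or earlier), or left out is absent from every risk set from Day 29 on. Kaplan-Meier and Cox estimates are identical in all four cases, so a floor of 1 day changes no result.

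**7. The binary endpoints.** With M = R − 1, Week 12 follows the medication and is non-response. It also follows a true start during treatment before the Week 12 assessment, so PASI75 is the same.

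**The case for a change.** The strongest reply is that pre-specification exists so that analysts need not infer intent. The fallback does not name this case, SAP Table 2 repeats the worst-value rule without any fallback, and Protocol 9.2.3 leaves the handling to the SAP. SAP 3.4.2 extends the approach to DLQI, which is measured only at baseline and Week 12. For DLQI, even a fully dated start before Week 12 leaves no eligible value unless there was an early end-of-treatment assessment.

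The textual part stands: the fallback wording is narrower than its evident use, and the formula has no floor. But step 3 resolves DLQI in the same way, to baseline and zero change.

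A missing month or year is the one route by which measured values or responses could be lost to any extent. Counting start days shows which dates are exposed, not how often this happens. Protocol 6.9 requires start and end dates in the eCRF and has participants report new medication between visits. An on-study start in a 12-week trial with month or year unknown should therefore be uncommon. The blinded review in SAP 3.2.2 also looks at timing before database lock, although Table 4 is redacted and its criteria cannot be checked.

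The contrast with binary non-response does not come from SAP 5.6. SAP 3.4.2 censors every user of a selected medication who has not yet responded, whatever the date quality. Keeping only imputed-date users event-free to the last assessment would treat them differently from a fully dated Day 40 starter, who is censored on Day 40. That is a debatable trade-off on an exploratory output.

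**Conclusion.** No change to the plan follows. The date arithmetic is right: a start imputed to the day before randomization leaves no eligible post-baseline PASI and gives 0 or fewer days at risk. In context, SAP 3.3.1.2 leads to baseline and 0% change, which is what an analyst would do anyway. In the SAP's example with the day missing, the time-to-response estimates do not depend on how the 0 is handled. In the least favourable calendar the exposure is 3 start days with a nominal Week 4 visit.

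What remains is a month or year missing for an on-study start. Its frequency is not given in the documents and should be low in view of the recording requirements. Where it occurs, the rule sets aside values before the true start, in the same way in every arm.

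The outputs concerned are PASI percent change, whose p-value is nominal under SAP 3.5, and exploratory endpoints for which SAP 3.4.2 presents no p-values. The conclusion assumes nominal visit days, first dose on the randomization day except where a lag is shown, and no early or unscheduled PASI.

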3.4 TERTIARY/EXPLORATORY ENDPOINT(S) ANALYSIS

The tertiary endpoints detailed in this section are:

[figure not shown]
- PASI percent change from baseline to Week 4 and 8
- The proportion of participants with a 50% or greater PASI reduction from baseline (PASI50) at Week 4, 8 and 12
- The proportion of participants with a 90% or greater PASI reduction from baseline (PASI90) at Week 4, 8 and 12
- The proportion of participants with a 100% PASI reduction from baseline (PASI100) at Week 4, 8 and 12
- The proportion of participants with PASI75 at Week 4 and 8

- [REDACTED]

- Time until the first achievement of PASI75
- Time until the first achievement of PASI90

- Change in Dermatology Life Quality Index (DLQI) from baseline to Week 12.

Other tertiary endpoints analyses are defined in [Section 3.6.2 \(AE, SAE\)](#), [Section 3.6.3.1 \(laboratory abnormalities\)](#), [Section 3.7.1.1 \(PK\)](#), [Section 3.7.1.2 \(quality of life\)](#), [Section 3.7.1.3 \(biomarkers\)](#).

In addition, the primary and secondary endpoints will be analyzed in ETIP population and ITT population for exploratory purpose.

